#### 5.2.6.2.2 AE reporting to the sponsor and timelines

The Investigator must report SAEs, and non-serious AEs which are relevant for the reported SAE, on the BI SAE form via fax immediately to the sponsor's unique entry point (country specific contact details will be provided in the ISF). The same timeline applies if follow-up information becomes available. In specific occasions the Investigator could inform the sponsor upfront via telephone. This does not replace the requirement to complete and fax the BI SAE form.

With receipt of any further information to these events, a follow-up SAE form has to be provided. For follow-up information, the same rules and timeline apply as for initial information.

#### 5.2.6.2.3 Information required

All (S)AEs, including those persisting after the individual subject's end of trial, must be followed up until they have resolved, have been sufficiently assessed as 'chronic' or 'stable', or no further information can be obtained.

### 5.3 DRUG CONCENTRATION MEASUREMENTS AND PHARMACOKINETICS

#### 5.3.1 Assessment of pharmacokinetics

For the assessment of pharmacokinetics, blood samples will be collected at the time points / time intervals indicated in the [Flow Chart](#). The actual sampling times will be recorded and used for determination of pharmacokinetic parameters.

#### 5.3.2 Methods of sample collection

##### 5.3.2.1 Blood sampling for pharmacokinetic analysis

For quantification of Nintedanib concentrations in plasma, approximately 2.7 mL of blood will be drawn from an antecubital or forearm vein into an K2-EDTA (dipotassium ethylenediaminetetraacetic acid)-anticoagulant blood drawing tube at the times indicated in the [Flow Chart](#). Blood will be withdrawn by means of either an indwelling venous catheter or by venepuncture with a metal needle. The first 0.5 mL withdrawn by an indwelling cannula will be discarded.

The EDTA-anticoagulated blood samples will be centrifuged for approximately 10 min at approximately 2000 g to 4000 g and at 4 to 8 °C. Two plasma aliquots will be obtained and stored in polypropylene tubes. The first aliquot should contain at least 0.5 mL of plasma. The process from blood collection until transfer of plasma aliquots into the freezer should be completed in less than 60 min with interim storage of blood samples and aliquots in ice water or on ice. The time each aliquot was placed in the freezer will be documented. Until transfer on dry ice to the analytical laboratory, the aliquots will be stored upright at approximately -20°C or below at the trial site. The second aliquot will be transferred to the analytical laboratory after the bioanalyst has acknowledged safe arrival of the first aliquot. At

the analytical laboratory, the plasma samples will be stored at approximately -20°C or below until analysis.

At a minimum, the sample tube labels should list BI trial number, subject number, visit, and planned sampling time.

After completion of the trial, the plasma samples may be used for further methodological investigations (e.g. for stability testing or assessment of metabolites. However, only data related to the analyte and/or its metabolite(s) including anti-drug antibodies (if applicable) will be generated by these additional investigations. The study samples will be discarded after completion of the additional investigations but not later than 5 years after the CTR is archived.

#### **5.3.4 Pharmacokinetic - pharmacodynamic relationship**

No analysis of the relationship between pharmacokinetic and pharmacodynamic parameters is planned for this trial.

#### **5.4 ASSESSMENT OF BIOMARKER(S)**

Not applicable.

#### **5.5 BIOBANKING**

Not applicable.

#### **5.6 APPROPRIATENESS OF MEASUREMENTS**

All measurements performed during this trial are standard measurements and will be performed in order to monitor subjects' safety and to determine pharmacokinetic parameters in an appropriate way. The scheduled measurements will allow monitoring of changes in vital signs, standard laboratory values, and ECG parameters that might occur as a result of administration of trial medication. The safety assessments are standard, are accepted for evaluation of safety and tolerability of an orally administered drug, and are widely used in clinical trials. The pharmacokinetic parameters and measurements outlined in Section [5.3](#) are generally used assessments of drug exposure.

## 6. INVESTIGATIONAL PLAN

### 6.1 VISIT SCHEDULE

Exact times of measurements outside the permitted time windows will be documented. The acceptable time windows for screening, the end of trial examination, and measurements and assessments scheduled to occur 'before' trial medication administration in the morning of Day 1 are provided in the [Flow Chart](#).

If not stated otherwise in the [Flow Chart](#), the general acceptable deviation from the scheduled time for vital signs, ECG, and laboratory tests will be  $\pm 30$  min.

The acceptable deviations from the nominal urine sampling time points for urinalysis are:

- The pre-dose urine sample will be the first void of the day or a sample collected  $\leq 3$  h before dosing
- Post-dose urine samples will be taken  $\pm 2$  h from the nominal urine sampling time

If scheduled in the [Flow Chart](#) at the same time as a meal, blood sampling, vital signs, and 12-lead ECG recordings have to be done first. Furthermore, if several measurements including venepuncture are scheduled for the same time, venepuncture should be the last of the measurements due to its inconvenience to the subject and possible influence on physiological parameters.

For planned blood sampling times, refer to the [Flow Chart](#). While these nominal times should be adhered to as closely as possible, the actual sampling times will be recorded and used for the determination of pharmacokinetic parameters.

If a subject misses an appointment, it will be rescheduled if possible. The relevance of measurements outside the permitted time windows will be assessed no later than at the Report Planning Meeting.

### 6.2 DETAILS OF TRIAL PROCEDURES AT SELECTED VISITS

#### 6.2.1 Screening period

After having been informed about the trial, all subjects will provide written informed consent in accordance with GCP and local legislation prior to enrolment in the study.

For information regarding laboratory tests (including drug and virus screening), ECG, vital signs, and physical examination, refer to Sections [5.2.1](#) to [5.2.4](#).

#### 6.2.2 Treatment periods

Each subject is expected to participate in 3 treatment periods (part 1, optional part 2) or in 2 treatment periods (optional part 3) (Days -1, 1, 2, 3, and 4 in each period). At least 14 days will separate drug administrations in each treatment periods.

In the evening before drug administration, study participants will be admitted to the trial site and kept under close medical surveillance for at least 72 h following drug administration in the morning of Day 1. The subjects will then be allowed to leave the trial site after formal

assessment and confirmation of their fitness. No ambulatory appointments are planned during treatment periods.

For details on time points and procedures for collection of plasma samples for PK analysis, refer to [Flow Chart](#) and Section [5.3.2](#).

The safety measurements performed during the treatment period are specified in Section [5.2](#) of this protocol and in the [Flow Chart](#). For details on times of all other trial procedures, refer to the [Flow Chart](#). AEs and concomitant therapy will be assessed continuously from screening until the end of trial examination.

### 6.2.3 Follow-up period and trial completion

For AE assessment, laboratory tests, recording of ECG and vital signs, and physical examination during the follow-up period, see Sections [5.2.1](#) to [5.2.6](#). Subjects who discontinue treatment before the end of the planned treatment period should undergo the EoT Visit.

All abnormal values (including laboratory parameters) that are assessed as clinically relevant by the investigator will be monitored using the appropriate tests until a return to a medically acceptable level is achieved. (S)AEs persisting after a subject's EoT Visit must be followed until they have resolved, have been sufficiently characterised, or no further information can be obtained.

For definition of 'end of the trial' refer to Section [8.6](#).

## 7. STATISTICAL METHODS AND DETERMINATION OF SAMPLE SIZE

### 7.1 STATISTICAL DESIGN – MODEL

The main objective of this trial is to investigate the relative bioavailability of several MR formulations of Nintedanib (Test, T) compared to ■■■ mg of Ofev® IR, twice daily (Reference, R) following oral administration on the basis of the primary and secondary pharmacokinetic endpoints, as listed in Section [2.1.2](#) and [2.1.3](#). The trial is designed to allow intra-subject comparisons and will be evaluated statistically by use of a linear model for logarithmically transformed PK endpoints.

A further objective is to evaluate and compare further pharmacokinetic parameters between the treatments. These pharmacokinetic parameters will be assessed by descriptive statistics.

The assessment of safety and tolerability is a further objective of this trial, and will be evaluated by descriptive statistics for the parameters specified in Section [2.2.2.2](#).

### 7.2 NULL AND ALTERNATIVE HYPOTHESES

The relative bioavailability of each of the MR formulations compared with ■■■ mg of Ofev® IR will be estimated by the ratios of the geometric means (test/reference), and their corresponding 2-sided 90% confidence intervals (CIs) will be provided. This method corresponds to the two one-sided t-test procedure, each at the 5% significance level. Since the main focus is on estimation and not testing, a formal hypothesis test and associated acceptance range is not specified.

### 7.3 PLANNED ANALYSES

#### Analysis sets

Statistical analyses for each crossover part will be based on the following analysis sets:

- Treated set (TS): The treated set includes all subjects who were randomised and treated with at least one dose of study drug. The treated set will be used for safety analyses.
- Pharmacokinetic parameter analysis set (PKS): This set includes all subjects in the treated set (TS) who provide at least one PK endpoint that was defined as primary or secondary and was not excluded due to a protocol deviation relevant to the evaluation of PK or due to PK non-evaluability (as specified in the following subsection ‘Pharmacokinetics’). Thus, a subject will be included in the PKS, even if he/she contributes only one PK parameter value for one period to the statistical assessment. Descriptive and model based analyses of PK parameters will be based on the PKS.

Adherence to the protocol will be assessed by the trial team. Important protocol deviation (IPD) categories will be suggested in the DV domain sheet, IPDs will be identified no later than in the Report Planning Meeting, and the IPD categories will be updated as needed.

### Pharmacokinetics

Plasma concentration data and parameters of a subject will be included in the statistical pharmacokinetic (PK) analyses if they are not flagged for exclusion due to a protocol deviation relevant to the evaluation of PK (to be decided no later than in Report Planning Meeting) or due to PK non-evaluability (as revealed during data analysis, based on the criteria specified below). Exclusion of a subject's data will be documented in the CTR.

Relevant protocol violations may be

- Incorrect trial medication taken, i.e. the subject received at least one dose of trial medication the subject was not assigned to
- Incorrect dose of trial medication taken
- Use of restricted medications

Plasma concentrations and/or parameters of a subject will be considered as non-evaluable, if for example

- The subject experiences emesis at any time during the labelled dosing interval.
- A predose concentration is  $>5\%$   $C_{max}$  value of that subject
- Missing samples/concentration data at important phases of PK disposition curve

Plasma concentration data and parameters of a subject which is flagged for exclusion will be reported with its individual values but will not be included in the statistical analyses. Descriptive and inferential statistics of PK parameters will be based on the PKS.

Only concentration values within the validated concentration range and actual sampling times will be used for the calculation of pharmacokinetic parameters. Concentrations used in the pharmacokinetic calculations will be in the same format provided in the bioanalytical report, (that is, to the same number of decimal places provided in the bioanalytical report).

#### **7.3.1 Primary endpoint analyses**

Each of the crossover parts will be analysed separately according to bellows description.

#### Primary analyses

The statistical model used for the analysis of the primary endpoint will be an analysis of variance (ANOVA) model on the logarithmic scale. That is, the PK endpoints will be log-transformed (natural logarithm) prior to fitting the ANOVA model. This model will include effects accounting for the following sources of variation: sequence, subjects within sequences, period and treatment. The effect 'subjects within sequences' will be considered as random, whereas the other effects will be considered as fixed. The model is described by the following equation:

$$y_{ijkm} = \mu + \zeta_i + s_{im} + \pi_j + \tau_k + e_{ijkm}, \text{ where}$$

$y_{ijkm}$  = logarithm of response measured on subject m in sequence i receiving treatment k in period j,

$\mu$  = the overall mean,

$\zeta_i$  = the  $i^{\text{th}}$  sequence effect,  $i = 1, 2, (3)$ ,

$s_{im}$  = the effect associated with the  $m^{\text{th}}$  subject in the  $i^{\text{th}}$  sequence,  
 $m = 1, 2, \dots, n_i$

$\pi_j$  = the  $j^{\text{th}}$  period effect,  $j = 1, 2, (3)$ ,

$\tau_k$  = the  $k^{\text{th}}$  treatment effect,  $k = 1, 2, (3)$ ,

$e_{ijkm}$  = the random error associated with the  $m^{\text{th}}$  subject in sequence  $i$  who received treatment  $k$  in period  $j$ .

where  $s_{im} \sim N(0, \sigma_B^2)$  i.i.d.,  $e_{ijkm} \sim N(0, \sigma_W^2)$  i.i.d. and  $s_{im}, e_{ijkm}$  are independent random variables.

Point estimates for the ratios of the geometric means (test/reference) for the primary endpoint (see Section [2.1](#)) and their two-sided 90% confidence intervals (CIs) will be provided.

For each endpoint, the difference between the expected means for  $\log(T)$ - $\log(R)$  will be estimated by the difference in the corresponding adjusted means (Least Squares Means). Additionally their two-sided 90% confidence intervals will be calculated based on the residual error from the ANOVA and quantiles from the t-distribution. These quantities will then be back-transformed to the original scale to provide the point estimate and 90% CIs for each endpoint.

#### Further exploratory analyses

The same statistical model as stated above will be repeated for the primary endpoint but with all sources of variation ('sequence', 'subjects within sequences', 'period', 'treatment') considered as fixed effects.

In addition to the model based approach all parameters will be calculated and analysed descriptively.

### **7.3.2 Secondary endpoint analyses**

The secondary endpoints (refer to Section [2.1.3](#)) will be calculated according to the relevant internal BI procedures and will be assessed statistically using the same methods as described for the primary endpoint.

#### 7.3.4 Safety analyses

Safety will be analysed based on the assessments described in Section [2.2.2.2](#). All treated subjects (TS, refer to Section [7.2](#)) will be included in the safety analysis. Safety analyses will be descriptive in nature and based on BI standards. No hypothesis testing is planned.

For all analyses, the treatment actually administered (= treatment at onset) to the subject will be used (any deviations from the randomised treatment will be discussed in the minutes of the Blinded Report Planning Meeting).

Treatments will be compared in a descriptive way. Tabulations of frequencies/proportions will be used to evaluate categorical (qualitative) data, and tabulations of descriptive statistics will be used to analyse continuous (quantitative) data.

Measurements (such as ECG, vital signs, or laboratory parameters) or AEs will be assigned to treatments (see Section [4.1](#)) based on the actual treatment at the planned time of the measurement or on the recorded time of AE onset (concept of treatment emergent AEs). Therefore, measurements planned or AEs recorded prior to first intake of trial medication will be assigned to the screening period, those between first trial medication intake and end of REP (see Section [1.2.3](#)) will be assigned to the treatment period. Events occurring after the REP but prior to next intake or end of trial termination date will be assigned to 'follow-up'. In case of two or more treatments, the follow-up will be summarized according to the previous treatment. These assignments including the corresponding time intervals will be defined in detail in the TSAP. Note that AEs occurring after the last per protocol contact but entered before final database lock will be reported to Pharmacovigilance only and will not be captured in the trial database.

Additionally, further treatment intervals (analysing treatments) may be defined in the TSAP in order to provide summary statistics for time intervals, such as combined treatments, on-treatment totals, or periods without treatment effects (such as screening and follow-up intervals).

Adverse events will be coded using the Medical Dictionary for Regulatory Activities (MedDRA). Frequency, severity, and causal relationship of AEs will be tabulated by treatment, system organ class, and preferred term. SAEs, AESIs (see Section [5.2.6.1](#)), and other significant AEs (according to ICH E3) will be listed separately.

Previous and concomitant therapies will be presented per treatment group without consideration of time intervals and treatment periods.

Laboratory data will be compared to their reference ranges. Values outside the reference range as well as values defined as possibly clinically significant will be highlighted in the listings. Additionally, differences from baseline will be evaluated.

Vital signs or other safety-relevant data will be assessed with regard to possible on-treatment changes from baseline.

Relevant ECG findings will be reported as AEs.

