#### 4.1.4 Drug assignment and administration of doses for each subject

This trial is an open-label, randomised, single-dose study in three parts.

All 30 subjects of trial part 1 will receive three treatments in randomised order as a three-period crossover design.

All 15 subjects of trial part 2 will receive three treatments in randomised order as three-period crossover design.

All 14 subjects of trial part 3 will receive two treatments in a randomised order as two-period crossover design.

##### Trial part 1

Trial part 1 consists of two parallel groups each with a three-way crossover study. All subjects of each group will receive the three treatments in randomised order. The treatments to be evaluated are outlined in Table 4.1.4: 1.

Table 4.1.4: 1 Dosage and treatment schedule for trial part 1

Trial Part	Treatment	Substance	Formulation	Unit strength	Dosage	Total dose
■	■	■	■	■	■	■
	■	■	■	■	■	■
	■	■	■	■	■	■
■	■	■	■	■	■	■
	■	■	■	■	■	■
	■	■	■	■	■	■

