## 4.2 OTHER TREATMENTS, EMERGENCY PROCEDURES, RESTRICTIONS

### 4.2.1 Other treatments and emergency procedures

There are no special emergency procedures to be followed. No additional treatment is planned. However, if adverse events require treatment, the investigator can authorise symptomatic therapy. In those cases, subjects will be treated as necessary and, if required, kept under supervision at the trial site or transferred to a hospital until all results of medical evaluations are acceptable.

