### 4.2.2 Restrictions

#### 4.2.2.1 Restrictions regarding concomitant treatment

In principle, no concomitant therapy is allowed. All concomitant or rescue therapies will be recorded (including time of intake on study days) on the appropriate pages of the CRF.

Drugs with a known hepatotoxicity profile (e.g., paracetamol or diclofenac) or medication with an increased risk for bleeding (e.g. acetylsalicylic acid) should be avoided during the entire study; if necessary, short term use of ibuprofen is acceptable.

Known inhibitors or inducers of P-gp and CYP3A activity should be avoided during the entire study due to drug-drug interaction potential with Nintedanib. Drugs that cause QT/QTc interval prolongation should also be avoided.

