7. PLANNED ANALYSIS

Each of the three possible trial parts was planned to be analysed separately. Cohort 1 and cohort 2 of trial part 1 will be presented in one table, but the reference group will be stratified to R (Cohort 1) and R (Cohort 2).

Safety analysis (refer to [Section 7.8](#)) will be performed by [REDACTED] and will be presented in Sections 15.1 to 15.4 of the CTR and in Appendix 16.2 and 16.1.13.1.

Inferential statistical analyses of PK endpoints (refer to [Section 7.4](#) and [Section 7.5.2](#)) will also be performed by [REDACTED] and will be presented in Section 15.5 of the CTR and in Appendix 16.1.13.3.

Descriptive data analysis of PK endpoints and concentrations will be performed by the department of Translational Medicine and Clinical Pharmacology (TMCP) at BI and will be presented in Section 15.6 of the CTR and in Appendix 16.1.13.5.

The format of the listings and tables will follow the BI standards (see BI-KMED-BDS-HTG-0045 [\(8\)](#)) with the exception of those generated for PK-calculations following BI standards for PK/PD analysis [\(9\)](#).

The individual values of all subjects will be listed, sorted by treatment sequence, subject number and visit. The listings will be included in Appendix 16.2 of the CTR.

For end-of-text tables, the set of summary statistics for non-PK parameters is:

N	number non-missing observations
Mean	arithmetic mean
SD	standard deviation
Min	minimum
Median	median
Max	maximum

For analyte concentrations and PK parameters, the following descriptive statistics will additionally be calculated:

Nobs	number of observations
CV	arithmetic coefficient of variation
gMean	geometric mean
gCV	geometric coefficient of variation
P10	10th percentile
Q1	1st quartile
Q3	3rd quartile
P90	90th percentile

The data format for descriptive statistics of concentrations will be identical to the data format of the respective concentrations. The descriptive statistics of PK parameters will be calculated using the individual values with the number of decimal places as provided by the evaluation

program. Then the individual values as well as the descriptive statistics will be reported with three significant digits in the CTR.

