7.2 CONCOMITANT DISEASES AND MEDICATION

Frequency tables are planned for this section of the report, based on the TS.

Concomitant diseases will be coded using the coding system of the Medical Dictionary for Drug Regulatory Activities (MedDRA). Medications will be coded using the World Health Organization Drug Dictionary (WHO-DD). The coding version number will be displayed as a footnote in the respective output.

The diagnoses and medications will be listed. Subjects without any concomitant diagnoses or concomitant therapies will be marked with a “No” in the respective column.

The relevance of the concomitant therapies to the evaluation of PK will be decided no later than at the RPM.

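### Concomitant therapies are summarised without regard to period in a crossover, so the table cannot show after which formulation a therapy was taken (minor)

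*Protocol*

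**What the plan says.** The display rule is in the safety analysis section of the protocol (7.3.4): "Previous and concomitant therapies will be presented per treatment group without consideration of time intervals and treatment periods".

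The design is a within-subject comparison. Protocol 4.1.4 says: "All 30 subjects of trial part 1 will receive three treatments in randomised order as a three-period crossover design".

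On therapy itself, protocol 4.2.2.1 begins: "In principle, no concomitant therapy is allowed". Protocol 4.2.1 allows an exception: "However, if adverse events require treatment, the investigator can authorise symptomatic therapy". What is taken is captured in detail (4.2.2.1): "All concomitant or rescue therapies will be recorded (including time of intake on study days) on the appropriate pages of the CRF".

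SAP 7.2 says of concomitant diseases and medication: "Frequency tables are planned for this section of the report, based on the TS". It does not say what the columns are, and it does not repeat or replace the protocol rule. It adds: "The diagnoses and medications will be listed". SAP 4 states that for part 1 everything planned in the protocol will be carried out, so the protocol rule stands.

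**The concern.** Within the same protocol section, adverse events and measurements are assigned to the treatment actually given, by time of onset or planned time of measurement. SAP 6.1 turns this into screening, on-treatment and follow-up phases for each treatment. Therapies are exempted from that logic, and no reason is given.

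Ignoring periods does little harm when each subject has one treatment. Here each subject is planned to have three, so the period is the only thing that links a therapy to a formulation. Once it is dropped, the summary cannot answer the descriptive question a reader would bring to it: was symptomatic treatment needed more often after the immediate-release capsule than after the modified-release tablets?

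That question has some relevance. Protocol 1.3 gives better gastro-intestinal tolerability as the hypothesised advantage of the modified-release tablets, and symptomatic therapy for adverse events is allowed. The data needed to answer it are already being collected.

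**Working it through.** The plan gives no figure to reproduce, and the documents give no rate of symptomatic therapy use. The check is therefore a reading of the rule under each meaning it could have, with an illustration on assumed rates.

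**Step 1: what a treatment group could be.** Neither document defines the term for this crossover.
- Protocol 4.1.3 uses it in its heading and then describes two groups of 15 and allocation to sequences, which suggests cohort or sequence.
- SAP 7.1, the section next to 7.2, summarises by sequence and in total.
- SAP 7.8.3 uses the term for vital signs by treatment.

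Both readings are open.

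**Step 2: columns are sequences or cohorts.** Each column mixes therapies taken after the reference and after both prototypes. There is no prototype column and no comparison by formulation.

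**Step 3: columns are treatments, all subjects complete.** Let pR be the probability of needing a therapy in the reference period and pM the probability in each prototype period, taken as independent. With periods ignored, a completer counts in every column if he took a therapy in any period:

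shown rate = 1 − (1 − pR)(1 − pM)²

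- pR = 20%, pM = 5%: 1 − 0.80 × 0.95² = 1 − 0.722 = 27.8% in all three columns. The true difference is 15 points; the difference shown is 0.
- pR = 40%, pM = 10%: 1 − 0.60 × 0.90² = 1 − 0.486 = 51.4% in all three columns. The true difference is 30 points; the difference shown is 0.

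The equality does not depend on the rates or on independence: the same subjects, with the same therapies, fill each column.

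**Step 4: columns are treatments, some subjects leave.** Suppose a fraction d leaves after period 1, spread evenly over the three sequences. Each leaver then counts only in the column of the treatment he received. The completers cancel, leaving

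difference shown = (pR − pM) × (d/3) / (1 − d + d/3)

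| d | multiplier | true 15 points shows as | true 30 points shows as |
|---|---|---|---|
| 10% | 0.0333/0.9333 = 0.036 | 0.5 | 1.1 |
| 20% | 0.0667/0.8667 = 0.077 | 1.2 | 2.3 |
| 50% | 0.1667/0.6667 = 0.250 | 3.75 | 7.5 |

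The difference is attenuated rather than removed, and even at 50% leaving three quarters of it is lost.

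**Step 5: attribution by period of intake.** Assigning each intake to its own period would show the assumed rates themselves: 20% against 5%, or 40% against 10%.

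**The case against.** The strongest case on the other side is that little depends on this table.

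- **Not an endpoint.** Protocol 2.2.2.2 assesses tolerability through adverse events, laboratory tests, ECG and vital signs. Adverse events are tabulated by treatment (SAP 7.8.1), so the gastro-intestinal comparison that motivates the tablets is kept. This stands.
- **The information is not lost.** Medications are listed individually, and SAP 7 says: "The individual values of all subjects will be listed, sorted by treatment sequence, subject number and visit". Intake times on study days are recorded, and adverse event records include any treatment given (protocol 5.2.6.2.1). SAP 4 reports 7 subjects in cohort 1 and 14 in cohort 2, few enough to read case by case. This stands, but it describes a workaround; the planned summary itself still cannot attribute a therapy.
- **PK is protected elsewhere.** Use of restricted medication is named as a possible PK-relevant violation (protocol 7.3), and SAP 7.2 has the PK relevance of therapies decided by the Report Planning Meeting. This stands.

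Three stronger inferences are tempting, and the documents do not support them.

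- A reader might infer that therapies taken after the reference will be printed under the modified-release tablets. That follows only if the columns are treatments; on the sequence or cohort reading there are no such columns.
- A reader might infer that any difference between formulations vanishes. Step 4 shows that exact cancellation needs complete follow-up as well as treatment columns. MR1 and MR2 prototypes are also given to different subjects, so columns from different cohorts need not agree.
- A reader might take a high rate of symptomatic treatment from the diarrhoea counts in protocol Table 1.2.2: 1. Some trials there are high (7/15, 14/36, 24/70), but others report 1/24, 1/13 or none. Over all nine the total is (7 + 0 + 14 + 1 + 0 + 7 + 0 + 24 + 1) / (15 + 8 + 36 + 24 + 31 + 26 + 17 + 70 + 13) = 54/240 = 22.5%. These are events, not treated events, and protocol 1.2.2 describes all drug-related events as mild or moderate and fully reversible.

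**Conclusion.** The point holds, and it is minor. On either reading of the protocol rule, the planned summary of concomitant therapies cannot show after which formulation a therapy was taken. SAP 7.2 does not repair this.

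The consequence is confined to one descriptive safety table. No primary or secondary PK result and no adverse event table depends on it.

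That the table cannot attribute a therapy follows from the design and the wording alone. The sizes shown rest on assumptions: treatment columns, illustrative rates of 20% against 5% and 40% against 10%, independence between periods, and leavers spread evenly over sequences. The documents do not say how many of the 7 and 14 subjects received all three treatments, so the amount of attenuation in the actual data is unknown.

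**What to change.** In protocol 7.3.4 and SAP 7.2, replace the rule with one that uses the time of intake:

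- Assign each therapy started on or after the first dose to the treatment phase of intake, using the recorded start date and time and the phases of SAP 6.1.
- Tabulate these therapies by actual treatment: MR1-1, MR1-2, MR2-1, MR2-2 and the reference, with the reference split by cohort as SAP 7 already does.
- Show therapies started before the first dose by sequence or in total.
- State how a therapy with an incomplete start time is assigned. SAP 6.6 refers to a standard for incomplete adverse event dates but names none for medication.

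If the protocol is no longer being amended, the departure can be recorded in SAP 4, which is the place for changes to the planned analysis.

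The cost is SAP wording and minor programming. No new data are needed.
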